5.5 Handling of Missing Data

Partially missing date of diagnosis needs to be imputed for calculating time from diagnosis to baseline. The following imputation rules will be applied:

- If only day is missing, impute as the first day of the month.
- If both day and month are missing, impute as Jan 1st.
- If year is missing, no imputation will be performed.

The above rules also apply to other diagnosis dates including date of metastatic disease, date of advanced disease, date of cancer surgery, radiation and prior cancer medications.

For partially missing additional cancer therapy date, the imputation is same as above except when only day is missing and the month is the same as in on-study progression date, in which case the day of additional cancer therapy will be imputed as the day of progression + 1 to avoid censoring a progression event due to an uncertain anticancer therapy start date.

For partially missing AE start dates (missing day and/or month), the following imputation rules will be applied:

- If both day and month of the AE start date are missing, the day and month will be imputed with the day and month of the first study dose date if the year is equal to the year of the first dose given the AE end date is not prior to first dose. Otherwise, the month and day is imputed as the first day of the year (Jan 1st).
- If only day is missing, and if the year and month are equal to the first dose date, the AE start date will be imputed as the first dose date given the AE end date is not prior to first dose. Otherwise, the day will be imputed as “01”. As a general consideration, imputed AE start date cannot be after AE end date if available.

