8 EFFICACY ANALYSES

8.1 Analyses of the Primary Endpoint

The primary endpoint is objective response rate (ORR). ORR will be estimated based on the proportion of evaluable subjects who achieve best overall response (BOR) of complete response (CR) or partial response (PR) per RECIST 1.1 that are confirmed at an interval of at least 28 days. The estimate of the objective response rate will be accompanied by one-sided and two-sided 95% Clopper-Pearson confidence intervals. For Cohort 1, a one-sample exact binomial test with one-sided significance level of 0.05 will be used to test the response rate under the null (H_0 : ORR=5%) and alternative (H_a : ORR=15%) hypotheses (5% vs. 15%, respectively). For each of Cohorts 2 and 3, the estimate of ORR will be compared with the fixed rates of 5% and 10% with one-sided significance level of 0.10. The primary ORR analysis is based on evaluable population and secondarily on Safety Population. The analysis of ORR will also be summarized for the PP population.

In this study, a minimum interval of 5 weeks from first dose date is required for stable disease (SD) status. Subjects with Not Evaluable (NE) or missing response will be treated as non-responders (i.e., they will be included in the denominator when calculating ORR).

Secondary analyses of ORR will include responses observed at a single time point (i.e., analysis of ORR will be summarized based on confirmed and unconfirmed CR or PR) based on Safety Population.

Waterfall plots will be used to depict graphically the maximum percent decrease from baseline in the sum of longest diameters of target lesions. A spider plot will be generated to depict changes in the sum of longest diameters of target lesions over time. A swimmer plot will also be used to show the effect of study treatment on tumor response for individual subjects.

Tumor assessment data after initiation of other anticancer therapy will be excluded for response related efficacy endpoints including BOR, DOR, PFS, waterfall plot, spider plot and swimmer plot.

For Cohorts 2 and 3, supplementary analyses of tumor response and progression will be performed using irRECIST criteria (in which new lesions do not necessarily constitute progression, but contribute to the calculated sum of diameter of all measurable disease). To be noted, if not all target lesions are measured at a visit, the sum of diameters should not be calculated.

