8.2 Analyses of Secondary Endpoints

8.2.1 PFS

Progression Free Survival (PFS) is defined as the time from the study treatment first dose to the earlier of disease progression or death due to any cause. Disease progression will be assessed using RECIST 1.1. The progression and censoring dates will be based on the May 2007 FDA Guidance for Industry, ‘*Clinical Trial Endpoints for the Approval of Cancer Drugs and Biologics*’. Determination rules for events or censored PFS is summarized in Table 2.

Table 2: Date of Event or Censoring for the Primary PFS analysis

Situation	Date of Event or Censoring	Outcome
Disease progression between scheduled disease assessments	Date of progression	Event
Death between scheduled disease assessment	Date of death	Event
Death before the first planned disease assessment at 6 weeks (plus 1 week window) without any disease assessment	Date of death	Event
No baseline disease assessments	Date of first dose	Censored
No post-baseline disease assessments without death before the first planned disease assessment	Date of first dose	Censored
Discontinuation of study treatment without progression (i.e., due to toxicity, withdrew consent, or lost to follow-up) and no further radiographic assessment ^a	Date of last radiological assessment	Censored
Alternate anticancer treatment started without documentation of disease progression beforehand ^b	Date of last radiological assessment prior to start of further anticancer treatment	Censored
Death or disease progression after missing two or more consecutively scheduled disease assessments ^c	Date of last radiological assessment without documented progression disease prior to death/progression	Censored
Patients who have not progressed and are alive	Date of last radiological assessment without documented progression disease	Censored

- For a patient who discontinues study treatment without PD and continues to have radiographic assessments, post-treatment radiographic assessments will be considered for PFS analyses according to the rules in this table.
- Alternate anticancer treatment interventions that are diagnostic (e.g. biopsy) or palliative (e.g., local radiation for painful nodule), as determined by medical review, will not routinely require censoring unless they are determined to interfere with the assessment of the patients’ disease status.

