8.2.2 Duration of response (DOR) and disease control rate (DCR)

Duration of Response (DOR) will be calculated for subjects who achieve confirmed CR or PR. For such subjects, DOR is defined as the time from response criteria are first met for either CR or PR, until the first date PD is objectively documented, or until death. DOR will be right-censored based on the same rules as described for PFS above.

DOR will be summarized descriptively and the median DOR will be estimated using the Kaplan-Meier method.

Swimmer plots will be provided depicting graphically the duration of response for patients who achieve complete response or partial response per RECIST 1.1 in each cohort. For Cohorts 2 and 3, swimmer plots of tumor response will also be provided per irRECIST criteria.

Disease control rate (DCR) is defined as the proportion of evaluable subjects who achieved BOR of CR or PR with any duration or SD with duration of at least 3 months (i.e., ≥ 3 months). The estimate of the DCR will be accompanied by one-sided and two-sided 95% Clopper-Pearson confidence intervals. Additionally, DOR and DCR will be derived and summarized based on the irRECIST criteria for Cohorts 2 and 3 subjects.

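### SAP 5.5 sets a year-only additional-therapy date to 1 January, so a later progression in that year is censored, which its own exception is meant to prevent

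*SAP*

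**What the plan says.** SAP 5.5 gives a general rule for partial dates: "If both day and month are missing, impute as Jan 1st". Additional cancer therapy follows the general rule with one departure: "the imputation is same as above except when only day is missing and the month is the same as in on-study progression date". In that case the therapy is dated one day after progression, and the SAP gives the reason: "to avoid censoring a progression event due to an uncertain anticancer therapy start date".

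Three later rules use the therapy date:

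- SAP 8.2.1, Table 2. The situation "Alternate anticancer treatment started without documentation of disease progression beforehand" is censored at the "Date of last radiological assessment prior to start of further anticancer treatment". A separate row censors patients without a post-baseline assessment at first dose, unless they died before the first planned one.
- SAP 8.1. "Tumor assessment data after initiation of other anticancer therapy will be excluded for response related efficacy endpoints including BOR, DOR, PFS", as well as the response plots.
- SAP 8.2.2. "DOR will be right-censored based on the same rules as described for PFS above".

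The adverse-event rule in SAP 5.5 is tied to first dose: when day and month are missing, "the day and month will be imputed with the day and month of the first study dose date if the year is equal". The therapy rule has no such tie to first dose, last dose or progression.

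**The concern.** A date with only the year known is more uncertain than one lacking only the day, yet only the latter is protected. For a year-only date the uncertainty is always resolved towards the earliest day of the year. If progression is in that year, therapy is placed ahead of it and an observed event is lost. The likelier order is often the reverse, because Protocol 10.1.4 ends scheduled tumor assessments once alternate therapy starts. A progression recorded on study will therefore usually have come first.

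At stake are PFS events, DOR events and, where the response is also in the known year, the response itself. A therapy date before first dose is also impossible on its face for a therapy recorded as additional to study treatment.

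**Working it through.** No sample size or error rate depends on this rule, so the check applies the SAP's rules to dates. The dates are invented for illustration, with scans every 42 days as in the 6-weekly schedule. Study day = date − first dose + 1.

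**Control: day missing, month known.** First dose 3 Oct 2016; scans 14 Nov 2016 (day 43), 26 Dec 2016 (day 85), 6 Feb 2017 (day 127) and 20 Mar 2017 (day 169, progression). Therapy is recorded as March 2017. The exception applies, therapy becomes 21 Mar 2017, and the event stays at day 169. The device works where it applies.

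**Example 1: year only, first dose in the year before.** Same patient, therapy recorded as 2017.
- Imputed therapy date: 1 Jan 2017, which is before progression on 20 Mar 2017.
- Last scan before it: 26 Dec 2016. PFS is censored at day 85 instead of an event at day 169.
- DOR, if a response was first seen on 14 Nov and confirmed on 26 Dec: the event 126 days after response (14 Nov to 20 Mar) becomes censoring at 42 days (14 Nov to 26 Dec).
- If the response was first seen on 26 Dec, its confirming scan on 6 Feb is excluded under SAP 8.1. The response is unconfirmed, the patient is a non-responder for the primary ORR and is not in the DOR set.

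**Example 2: year only, first dose in the same year.** First dose 2 Mar 2017; scans 13 Apr, 25 May, 6 Jul and 17 Aug 2017 (day 169, progression). Therapy is recorded as 2017.
- Imputed therapy date: 1 Jan 2017, which is 30 + 28 + 2 = 60 days before first dose.
- All four scans fall after it and are excluded. The Table 2 row for patients without a post-baseline assessment applies, so PFS is censored at first dose (day 1) instead of an event at day 169.
- Any response in this patient is excluded as well. SAP 8.1 counts missing or non-evaluable response as non-response.

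**How general this is.** Among the 365 possible progression dates in a non-leap known year, 1 January is strictly earlier for 364; a progression on 1 January is a tie. If first dose is also in that year, the imputed date precedes it for 364 of 365 first-dose dates.

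**Where it does no harm.** If progression was in an earlier year than the therapy, 1 January falls after progression and the event is kept.

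**The case against.** The strongest reply is that such records should hardly occur. Anti-cancer medications are recorded throughout follow-up, the End of Treatment visit comes before alternate therapy, sites are asked to scan before any intervention, and case report forms are checked against source. This stands as an argument about frequency. It does not exclude the case, because follow-up after progression is every 12 weeks and may be by telephone, and the SAP itself saw a need for partial-date rules.

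Two further points stand. Table 2 does not routinely censor for interventions judged diagnostic or palliative on medical review. If the therapy truly began before progression, censoring is the intended result; the fault is that an unknown order is always resolved that way.

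A reader might infer more than the documents support:

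- That the SAP leaves Example 2 undefined. It does not; the row for no post-baseline assessment fits.
- That DOR is always censored. It is censored only when the response, including its confirmation, predates 1 January; otherwise the response is lost.
- That each record costs 1 of 36 events in Cohort 1. The 36 is a power assumption for the Cox model of gpNMB expression in 52 evaluable patients (Protocol 11.5.1). PFS is analyzed in all treated patients, about 60 in that cohort.
- That the primary result could be inflated. Excluding scans can only remove responses.

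**Conclusion.** The point holds as an error in a stated rule. Followed literally, SAP 5.5 censors a progression because the therapy date is uncertain, which is what its exception says it avoids. It can also produce a therapy date before first dose.

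The size is minor. The documents do not give the number of affected records, and it is probably small. PFS and DOR are secondary and summarized descriptively, no power loss is claimed, and the effect on ORR is conservative. The conclusion assumes that a year-only additional-therapy date is recorded, that progression falls after 1 January of that year, and that the therapy is one that Table 2 would censor for. The day-only rule is not in question.

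**What to change.** In SAP 5.5, for additional-therapy dates with day and month missing, impute the latest of:

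- 1 January of the known year;
- last study dose date + 1, if that dose is in the known year;
- on-study progression date + 1, if progression is in the known year.

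Cap the result at the end of the known year, death or last contact, and count a progression on the imputed date as before therapy. The tie rule is needed only when a cap applies, for example progression on 31 December. Leave the day-only, diagnosis and prior-therapy rules unchanged. A known year earlier than the year of the last study dose is not settled by this rule and should be queried.

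If the last study dose was before progression, the imputed dates become 21 Mar 2017 (Example 1) and 18 Aug 2017 (Example 2), and both progressions stay events at day 169. The last-dose term also helps a responder with no progression in the known year: scans up to the last dose are kept.

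Add a sensitivity analysis of ORR, PFS and DOR that uses the earliest possible therapy date, not before first dose.

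The cost is a few sentences, a small programming change and one extra run. The downside is that a therapy which truly began before progression, or before a confirming scan, could let that event or response count in the main analysis. At the Cohort 1 boundary this could matter: with n = 52 and a null rate of 5%, the exact one-sided p-value is 0.1174 for 5 responses and 0.0445 for 6 (the SAP's 0.045). The earliest-date analysis shows whether any conclusion depends on it.

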6 STUDY SUBJECTS

6.1 Disposition and Withdrawals

Subject disposition will be summarized by treatment cohort based on Safety Population. Disposition of subjects includes the number and percentage of subjects for the following categories: subjects who were treated, subjects who discontinued treatment, subject survival status, and subjects who discontinued from the study, with percentages based on the relevant cohort.

The reasons for study discontinuation and treatment discontinuation will also be summarized.

Subject disposition data will be presented in a data listing.

6.2 Protocol Deviations

The important protocol deviations and the Per Protocol (PP) population will be determined prior to the database lock. Protocol deviations will be listed by treatment cohort, patient number, and categorized according to the deviation reasons. All important protocol deviations will also be presented in a data listing.

7 DEMOGRAPHICS AND BASELINE CHARACTERISTICS

Unless specified otherwise, the baseline values will be those values measured closest to but not after the first dose of study treatment.

A summary of demographics and baseline information will be presented by study cohort. Continuous data will be summarized using number, mean, standard deviation (SD), median, Q1, Q3, minimum, and maximum. Categorical and ordinal data will be summarized using number and percentage of subjects in each treatment cohort. Percentages will be based on the total number of subjects in the Safety Population.

Subject demographic and baseline characteristics will also be presented in a listing.

7.1 Demographics

The following demographic variables will be summarized:

- Age (years)
- Age category (≤ 18 , 19 - 64, ≥ 65)
- Sex (male or female)
- Race (White, Black or African American, Asian, American Indian or Alaska Native, Native Hawaiian or Other Pacific Islander, Other)
- Ethnicity (Hispanic or Latino, Not Hispanic or Latino)
- Height (cm)
- Weight (kg)
- Body Mass Index (kg/m^2)
- Baseline ECOG performance status (0, 1)

7.2 Disease Characteristics

The following baseline disease characteristics will be summarized:

- Time since initial diagnosis (years)
- Stage at initial diagnosis
- Stage at study entry
- Metastasis staging at study entry
- Histopathologic Type
- Mutations (BRAF, BRAF types and other mutations)
- Number of organs (disease sites) involved
- Most frequent disease site
- Historical or current CNS involvement
- Time since advanced and/or metastatic disease (calculated relative to first dose date)
- Number of Subjects with at Least One Additional Relapse or Disease Progression

- Tumor burden as measured by sum of diameter
- Elevated Lactate Dehydrogenase (LDH) (Yes, No)
- Cohort 3 only: PD-L1, positive (positive in $\geq 1\%$ tumor cells) vs negative
- % positive gpNMB in epithelial cells (descriptive statistics and categories: 100% vs $< 100\%$)

7.3 Prior Therapy and Medical History

Prior medical and surgical history will be coded by MedDRA (Medical Dictionary for Regulatory Activities) and will be summarized by treatment cohorts.

The following prior anti-cancer treatment parameters will be summarized:

- Number of prior systemic anti-cancer regimens
- Prior cancer treatment class: check point inhibitor (CPI) with subcategories including CTLA-4 and PD-1/PD-L1, other immunotherapy, BRAF related TKI, cytokines and cytotoxic-containing therapy
- Number of prior CPI containing regimens
- Best response to first prior CPI treatment
- Best response to and duration of last prior CPI treatment
- Surgery/Biopsy description (Resection, Biopsy or Other)
- Prior radiation therapy (Yes or No)
- Prior cancer surgeries (Yes or No, biopsy excluded)
- Time from last anti-cancer therapy to first dose of glembatumumab vedotin (≤ 2 or > 2 months)
- Time from CPI as last anti-cancer therapy to first dose of glembatumumab vedotin (≤ 2 months, > 2 month to ≤ 6 months, or > 6 months)

7.4 Prior and Concomitant Medications

All medications will be documented on the case report form (CRF) if taken within 28 days prior to the first dose of study treatment through (whichever occurs first) either a) 28 days after the last dose of study treatment, or b) initiation of alternate anticancer therapy. In addition, all anticancer therapies should be recorded throughout the duration of study follow-up.

All medications will be coded using the World Health Organization (WHO) drug dictionary. Prior medications are defined as medications that received before the first dose of study drug. Concomitant medications are defined as medications that (1) started before the first dose of study drug and were continuing into the treatment period, or (2) started on or after the date of the first dose of study drug up to 28 days after last dose.

The number (%) of subjects who took prior and concomitant medications will be summarized on the anatomical class (ATC) and preferred term (PT) by dose cohorts. A summary of concomitant anti-cancer therapies will be summarized separately by PT.

8 EFFICACY ANALYSES

8.1 Analyses of the Primary Endpoint

The primary endpoint is objective response rate (ORR). ORR will be estimated based on the proportion of evaluable subjects who achieve best overall response (BOR) of complete response (CR) or partial response (PR) per RECIST 1.1 that are confirmed at an interval of at least 28 days. The estimate of the objective response rate will be accompanied by one-sided and two-sided 95% Clopper-Pearson confidence intervals. For Cohort 1, a one-sample exact binomial test with one-sided significance level of 0.05 will be used to test the response rate under the null (H_0 : ORR=5%) and alternative (H_a : ORR=15%) hypotheses (5% vs. 15%, respectively). For each of Cohorts 2 and 3, the estimate of ORR will be compared with the fixed rates of 5% and 10% with one-sided significance level of 0.10. The primary ORR analysis is based on evaluable population and secondarily on Safety Population. The analysis of ORR will also be summarized for the PP population.

In this study, a minimum interval of 5 weeks from first dose date is required for stable disease (SD) status. Subjects with Not Evaluable (NE) or missing response will be treated as non-responders (i.e., they will be included in the denominator when calculating ORR).

Secondary analyses of ORR will include responses observed at a single time point (i.e., analysis of ORR will be summarized based on confirmed and unconfirmed CR or PR) based on Safety Population.

Waterfall plots will be used to depict graphically the maximum percent decrease from baseline in the sum of longest diameters of target lesions. A spider plot will be generated to depict changes in the sum of longest diameters of target lesions over time. A swimmer plot will also be used to show the effect of study treatment on tumor response for individual subjects.

Tumor assessment data after initiation of other anticancer therapy will be excluded for response related efficacy endpoints including BOR, DOR, PFS, waterfall plot, spider plot and swimmer plot.

For Cohorts 2 and 3, supplementary analyses of tumor response and progression will be performed using irRECIST criteria (in which new lesions do not necessarily constitute progression, but contribute to the calculated sum of diameter of all measurable disease). To be noted, if not all target lesions are measured at a visit, the sum of diameters should not be calculated.

As a secondary exploratory analysis, BOR and ORR by irRECIST criteria will be derived and summarized in a similar fashion as in the primary analyses. Specifically, for Cohorts 2 and 3, ORR will be compared with reference levels of 5% and 10%. One-sample exact binomial test with one-sided significance level will be provided for each test. Waterfall plots, spider plots and swimmer plots will be used to depict graphically the maximum percent decrease from baseline, changes in tumor burden (sum of longest diameters of target lesions and new lesions) over time and the effect of study treatment on tumor response, by irRECIST criteria for individual subjects.

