 - When no imaging/measurement is done at all at a particular time point, the patient is not evaluable (NE) at that time point.
 - If only a subset of lesion measurements are made at an assessment, usually the case is also considered NE at that time point, unless a convincing argument can be made that the contribution of the individual missing lesion(s) would not change the assigned time point response. This would be most likely to happen in the case of PD. For example, if a patient had a baseline sum of 50mm with three measured lesions and at follow-up only two lesions were assessed, but those gave a sum of 80 mm, the patient will have achieved PD status, regardless of the contribution of the missing lesion.
- 'Symptomatic deterioration': Patients with a global deterioration of health status requiring discontinuation of treatment without objective evidence of disease progression at that time should be reported as 'symptomatic deterioration'. Every effort should be made to document objective progression even after discontinuation of treatment. Symptomatic deterioration is not a descriptor of an objective response: it is a reason for stopping study therapy. The objective response status of such patients is to be determined by evaluation of target and non-target disease as shown in [Appendix 3 Table 1](#) and [Appendix 3 Table 2](#).

- In some circumstances it may be difficult to distinguish residual disease from normal tissue. When the evaluation of complete response depends upon this determination, it is recommended that the residual lesion be investigated (fine needle aspirate/biopsy) before assigning a status of complete response. FDG-PET may be used to upgrade a response to a CR in a manner similar to a biopsy in cases where a residual radiographic abnormality is thought to represent fibrosis or scarring.
- For equivocal findings of progression (e.g. very small and uncertain new lesions; cystic changes or necrosis in existing lesions), treatment may continue until the next scheduled assessment. If at the next scheduled assessment, progression is confirmed, the date of progression should be the earlier date when progression was suspected.
- Confirmation of response: In the event of complete or partial responses, efforts should be made to obtain a confirmatory scan (no sooner than 28 days later).

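### The SAP's irRECIST rule for partly measured visits omits the progression exception in Appendix 3, so progression shown by the measured lesions alone can be dated late or go uncounted in Cohorts 2 and 3

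*SAP*

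**What the plan says.** SAP section 8.1 says that for Cohorts 2 and 3 "supplementary analyses of tumor response and progression will be performed using irRECIST criteria". New lesions do not necessarily count as progression there; they are added to the sum instead. The same paragraph ends with the instruction that "if not all target lesions are measured at a visit, the sum of diameters should not be calculated". No exception follows. The next paragraph describes the irRECIST plots as showing "changes in tumor burden (sum of longest diameters of target lesions and new lesions) over time".

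Protocol Appendix 3, in its notes on missing assessments, deals with the same situation under RECIST 1.1. Its default is similar: "If only a subset of lesion measurements are made at an assessment, usually the case is also considered NE at that time point". It then makes an exception where a convincing argument exists that "the contribution of the individual missing lesion(s) would not change the assigned time point response", and says this is most likely for progression. In the worked example, three lesions total 50 mm at baseline and only two of them are measured later; because "those gave a sum of 80 mm, the patient will have achieved PD status, regardless of the contribution of the missing lesion".

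On scope, SAP section 2.2.3 lists irRECIST ORR and PFS as exploratory, section 5 applies irRECIST as a secondary analysis to every efficacy endpoint except OS, and section 8.2.2 adds irRECIST DOR and DCR. The main PFS analysis in section 8.2.1 uses RECIST 1.1.

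**The concern.** An unmeasured lesion can only add to a sum. If the lesions that were measured already put the patient over the progression limit, the missing one cannot reverse that. A rule that withholds the sum at such a visit withholds a progression that the scan has shown.

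irRECIST is more exposed to this than RECIST 1.1. Under RECIST 1.1 a new lesion is progression in itself, whereas under irRECIST it mainly feeds the sum. Without the sum, growth in measured new lesions at that visit is set aside as well.

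At stake is the comparison that the supplementary analysis exists to make. The investigator may record RECIST 1.1 progression from a scan at which irRECIST has no sum, so the two sets of results would differ for a computational reason. The error runs one way, towards later irRECIST progression.

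**Working it through.** **Inputs.** Baseline 50 mm on three lesions and follow-up 80 mm on two (Appendix 3, missing assessments). RECIST 1.1 progression: at least 20% and at least 5 mm above the smallest sum on study (Appendix 3, target lesions). Scans every 6 (±1) weeks for 6 months, then every 9 (±2) weeks (SAP section 8.2.1, notes to Table 2). Thirty patients enrolled and 25 evaluable per cohort (SAP section 3). Neither document states an irRECIST progression limit, so 20% and 5 mm is an assumption borrowed from Appendix 3.

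**1. The plan's own example.** Take 50 mm as the smallest sum. Limit = max(1.20 × 50, 50 + 5) = max(60, 55) = 60 mm. The partial sum of 80 mm is 80/50 − 1 = 60% and 80 − 50 = 30 mm above it. Progression is confirmed, as Appendix 3 says, and would hold for any relative limit up to 60%.

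**2. Why a partial sum is safe for progression.** Full sum = partial sum + missing diameters, and each missing diameter is at least 0 mm. So full sum ≥ partial sum. If the partial sum reaches the limit, the full sum does too.

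**3. Why it is not safe for response.** A partial response needs a sum of at most 0.70 × 50 = 35 mm. Two lesions totalling 35 mm would appear to qualify, yet any third lesion above 0 mm takes the full sum over 35 mm. Appendix 3 warns against leaving a lesion out of follow-up sums for this reason. The SAP rule is therefore right for CR, PR and SD, and the gap is confined to progression.

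**4. Timing under the SAP sentence.** With no sum at the partly measured visit, the earliest sum-based irRECIST progression is at the next complete scan.

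| Period | Nominal delay | With visit windows |
|---|---|---|
| First 6 months | 6 weeks | 6 − 2×1 = 4 to 6 + 2×1 = 8 weeks |
| Thereafter | 9 weeks | 9 − 2×2 = 5 to 9 + 2×2 = 13 weeks |

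The delay can be shorter still for a patient treated past apparent progression, because the next scan may then be brought forward.

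**5. When the event goes uncounted.** Scheduled scans stop at documented progression or at new anticancer therapy, and SAP section 8.1 excludes scans after new therapy. If the partly measured scan is the last before new therapy, no complete scan follows. If Table 2 of section 8.2.1 is carried over to irRECIST, which the SAP does not say, that patient is censored for irPFS while having an event under RECIST 1.1.

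**6. Effect on irDCR.** Section 8.2.2 requires SD of at least 3 months. A patient with SD at week 6 and provable progression at week 12 (84 days) falls short. If week 12 has no sum and progression is first scored at week 18 (126 days), the patient can qualify, provided SD duration runs to progression, which the SAP does not define. One such patient moves irDCR by 1/25 = 4 percentage points.

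**7. Frequency.** The documents give none. If 2%, 5% or 10% of patients were affected (assumed), that is 0.6, 1.5 or 3 of 30 per cohort.

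**8. What does not move.** Primary ORR and main PFS use RECIST 1.1, and the sample-size calculations in SAP section 3 do not rest on irRECIST. For irORR, section 8.1 counts not-evaluable or missing responses as non-response and derives the irRECIST rate similarly, so withholding a sum creates no responder.

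**The case against.** The strongest defence is that the two texts do not conflict. Appendix 3 is written for RECIST 1.1 and the SAP sentence sits in the irRECIST paragraph. Appendix 3's own default for a partly measured visit is not evaluable, and its exception depends on a case-by-case argument. The SAP sentence follows that default and guards against false responses. All of this stands. A reader might infer that the SAP contradicts Appendix 3; what the documents show is one exception not carried across.

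The SAP sentence also restricts a calculation, not a classification. It does not call the visit not evaluable or free of progression, and it does not exclude progression by another route, such as non-target disease. This stands too, so irRECIST progression can be delayed or missed, not that it always is. The defence does not supply a rule for the sum-based case, and the SAP has no irRECIST time-point algorithm to fill the gap.

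Three other stronger readings also fail:

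- **Delay of at least one full scan interval.** The visit windows allow 4 or 5 weeks between scans.
- **The irPFS event is always lost without a later scan.** Death is itself a PFS event in Table 2, subject to its censoring rules, so an event may still be recorded, only later.
- **irRECIST response rates are inflated.** The rule blocks responses based on partial sums, so it is if anything conservative for irORR.

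Finally, all target and non-target sites should normally be evaluated at every assessment, so such visits may be uncommon, and the endpoints concerned are supplementary. This limits the importance of the point but does not remove it.

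**Conclusion.** The point holds within narrow limits. For irRECIST in Cohorts 2 and 3, following SAP section 8.1 as written can discard sum-based progression that the measured lesions already prove. The consequence is a favorable bias in irPFS, in irDOR among responders, and in irDCR. Per affected patient it is a delay on the scale of one scan interval, or an event that is not counted. The overall size cannot be given, because the documents do not say how often a visit is partly measured with the remaining lesions already over the limit.

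The conclusion rests on irRECIST progression being judged mainly on the sum, and on the limit being no higher than what the measured lesions reach. It does not depend on the 20% and 5 mm figures as such. It does not touch the primary ORR test, its power or the main PFS analysis. The correction is worth making because the bias has one direction and the remedy is cheap.

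**What to change.** Keep the existing rule for CR, PR, SD and the waterfall plots, and add to SAP section 8.1:

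> If the measured target lesions plus measurable new lesions alone already meet the irRECIST limit for progression relative to the nadir, the time point is classed as progression on that date, and the partial sum is used as a lower bound.

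State that limit in the SAP. If 20% and 5 mm is intended, say that it is adopted from Appendix 3, since neither document gives it for irRECIST. State also which event and censoring dates apply to irPFS, because Table 2 is written for RECIST 1.1.

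The cost is one sentence for the exception, a few lines for the limit and dates, and one programming condition. No new data are needed. The downside is that irPFS becomes slightly less favorable.
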